## 5 STUDY POPULATION CHARACTERISTICS

### 5.1 Subject disposition

The number of subjects screened, and reason for screen failure will be summarized for all screened subjects. The disposition of screened subjects will also be presented including the date of the first and last subject into the study by region and site and number of subjects in each population by region and site.

The number of subjects randomized, completed Visit 28/Week 52, entered SFE, completed SFE, prematurely discontinued double-blind study treatment, prematurely discontinued from the study (by phase [main/SFE] and period [DB/OL-CZP/OL-OT]), and reason for premature discontinuation of study treatment and phase (main/SFE) will be summarized by treatment group. The number of subjects who complete each visit (as captured in the eCRF) will also be summarized. In addition, the number of subjects in each of the analysis sets, as specified in [Section 3.5](#), will be summarized as well.

### 5.2 Protocol deviations

The process for reviewing and identifying important protocol deviations is outlined in [Section 3.4](#). The number of subjects with at least one important protocol deviation will be summarized by treatment group in addition to whether that protocol deviation led to exclusion from the PPS.

The subject data listing, in contrast to the general approach (i.e., sorted by treatment group, region, site, subject number), will be sorted by region, site, treatment group, and subject number.

## 6 DEMOGRAPHICS AND OTHER BASELINE CHARACTERISTICS

The demographics and other Baseline characteristics will be presented for the RS. If the RS differs from the SS or the FAS, then demographics and Baseline characteristics tables may be repeated separately for these analysis sets. These summaries will be presented by treatment group and all subjects.

Tables on medical history and prior diseases, and concomitant and prior medications will also be presented.

## 6.1 Demographics

The following continuous demographic variables will be summarized:

- Age (years)
- Weight (kg)
- Height (cm)
- BMI (kg/m^2)

The following categorical demographic variables will also be summarized:

- Gender (Female, Male),
- Race (American Indian / Alaskan Native, Asian, Black, Native Hawaiian or Other Pacific Islander, White, Other / Mixed),
- Ethnicity (Hispanic or Latino, Not Hispanic or Latino),
- Racial subgroup (White, Other),
- Age class (to be summarized 3 ways: 1) 18-<65, 65-<85 and >=85; 2) ≤18, >18 to <65 years, and ≥65 years; and 3) 18 – <45 years, 45 – <65 years, ≥65 years),
- BMI class (<18.5 kg/m^2, 18.5 kg/m^2 to <25 kg/m^2, 25 kg/m^2 to <30 kg/m^2, ≥30 kg/m^2)

## 6.2 Other Baseline characteristics

In this section, the variables that will be summarized as Baseline characteristic are described.

The different binary items of the ASAS criteria will be presented in frequency tables:

- back pain of ≥ 3 month duration and age of onset < 45 (and per inclusion criteria back pain of ≥ 12 month duration and age of onset < 45)
- active (acute) inflammation on MRI highly suggestive of sacroiliitis associated with SpA
- HLA-B27 positivity (current features)
- inflammatory back pain (history and current features)
- arthritis (history and current features)
- enthesitis (history and current features)
- uveitis (history and current features)
- dactylitis (history and current features)
- psoriasis (history and current features)
- Crohn's disease/ ulcerative colitis (history and current features)
- elevated CRP (history and current features)

Symptom duration (calculated as described in [Section 4.8](#)) and time since diagnosis of disease will be summarized as continuous variables and dichotomized into <5 years and  $\geq 5$  years. Time since diagnosis of disease will be defined as: Earliest start date of the medical history (lower level term) of Axial Spondyloarthritis – date of first study medication administration. If a subject does not have a history of ‘Axial Spondyloarthritis’, then the time since diagnosis of disease will be set equal to the symptom duration.

Frequency tables will be provided for the following Baseline variables related to TB status:

- Contact with an individual with active TB
- Contact with an individual who has recently been treated for TB

Summary statistics will be provided for the laboratory variable CRP. Additionally, CRP at Baseline will be categorized based on the number of subjects with CRP  $\leq$ ULN and  $>$ ULN at Baseline.

Frequency tables will summarize HLA-B27, the test at Screening to rule out hepatitis B surface antigen, and the test at Screening to rule out antibodies to hepatitis C.

Frequencies will also be provided for subjects with the following:

- Peripheral arthritis (swollen joint count  $> 0$ ) at Baseline
- Enthesitis (MASES  $> 0$ )
- Extra-articular manifestations:
  - History of uveitis
  - History of psoriasis
  - History of IBD
- Concomitant DMARDs at Baseline
- Prior DMARDs and prior NSAIDs
- MRI/CRP classification (presented as used for stratification at IXRS randomization and as found in the source data along with a cross tabulation to display the number of misclassifications):
  - MRI+/CRP+
  - MRI+/CRP-
  - MRI-/CRP+
- Baseline cardiovascular risk elements (such as smoking, caffeine, and alcohol use)

Note that the term DMARDs is used above as it is common to rheumatic diseases. However, there is currently no conclusive evidence that DMARDs are in fact disease-modifying in axSpA (unlike in RA). As a result, the term SAARDs (slow-acting anti-rheumatic drugs) is used in the protocol to refer to this class of medications. The DMARDs terminology is generally used in this SAP, but it is recognized that SAARDs may be more appropriate in the context of a study of subjects with axSpA.

Since the procedures and surgeries in the procedural history will not be coded, these data will only be presented in listings.

Baseline information for other key measures related to axSpA (eg, BASFI, BASDAI, BASMI, and ASDAS) will be presented in the respective tables providing descriptive statistics over time.

### 6.3 Medical history and concomitant diseases

Previous and ongoing medical history will be summarized by MedDRA® system organ class (SOC) and preferred term (PT). Medical procedures are not coded. Concomitant diseases will be recorded by the Investigator at the Screening visit only.

### 6.4 Prior and concomitant medications

Prior medications include any medications that started prior to the start date of double-blind study medication. Past medications are a subset of prior medications, and include prior medications with a stop date before the date of first double-blind study medication administration.

Concomitant medications will be assigned to treatments according to whether they were taken at least one day in common with the treatment dosing period of that treatment as described in [Table 6–1](#). Dosing periods are defined as follows:

- For double-blind period: From first administration of double-blind medication to last administration of double-blind medication +14 days or first administration of open-label CZP, open-label other treatment or SFE period treatment, whatever comes first.
- For open-label CZP period: From first administration of open-label CZP medication to last administration of open-label CZP medication +14 days or first administration of open-label other treatment or SFE period treatment, whatever comes first.
- For open-label other treatment period: From first administration of open-label other treatment medication to last administration of open-label other treatment medication.
- For SFE period: From first administration of SFE period treatment to last administration of SFE period treatment + 14 days.

A medication can be defined as both prior and concomitant and can be concomitant to more than one treatment. Where a medication start or stop date is (partially) missing, the medication will be considered a concomitant medication, if there is the possibility of concomitant use according to the rules described in [Section 4.2.4](#). Hence, if a partial date implies the concomitant medication could have been taken concomitant to multiple treatments, it will be concomitant to all applicable treatments.

Table 6-1: Assignment of Concomitant Medications to treatments		
Period	Description	Treatment
Double-blind treatment	
 
1) If the start or end date of the concomitant medication falls into the double-blind dosing period or
 
2) if the concomitant medication starts prior to double-blind dosing period and ends after the double-blind dosing period or is ongoing,
 
 then assign to the double-blind treatment.	Summarized according to randomized CZP 200mg Q2W or PBO.  For subjects randomized to CZP 200mg Q2W, also include the medications in Total CZP incl DB and OL.  All double-blind period medications will be included in an All subjects summary.
Open-label CZP treatment	
 
1) If the start or end date of the concomitant medication falls into the OL-CZP dosing period or
 
2) if the concomitant medication starts prior to the OL-CZP dosing period and ends after the OL-CZP dosing period or is ongoing,
 
 then assign to the OL- CZP treatment.	Summarized according to CZP 200mg Q2W or PBO followed by open-label CZP (i.e. CZP->OL CZP or PBO->OL CZP). All open-label CZP period medications will also be included in a Total CZP incl DB and OL and an All subjects summary.
Open-label other treatment (OL-OT)	
 
1) If the start or end date of the concomitant medication falls into the OL-OT dosing period or
 
2) if the concomitant medication starts prior to the OL-OT dosing period and ends after the OL-OT dosing period or is ongoing,
 
 then assign to the OL-OT.	Only included in an All subjects summary.
Safety Follow-up Extension treatment	If the start date of the concomitant medication falls into the SFE dosing period then assign to the SFE treatment.  Note: Concomitant medication information is not systematically recorded during the SFE period. Only concomitant medication taken due to an adverse event will be documented in the CRF during that period. Only new medication starting during the SFE dosing period will therefore be considered.	Not summarized in tables

If a medication starts on the start date of a new dosing period, it will be considered concomitant to the treatment of that new period, but not to the treatment of the previous dosing period (even if the end date of the corresponding dosing period is on the same day as the start of the new dosing period.).

If a medication stops on the start date of a new dosing period it will not be considered concomitant to the treatment of that new dosing period, unless start and stop date of the medication are on the same date.

Past medication summaries will be generated for DMARDs, NSAIDs, and Anti-TNFs by ATC code (level 3 (4-digit) decode, level 4 (5-digit) decode, and Preferred Term).

Prior DMARDs and NSAIDs will be summarized by WHO-DRL ATC code (level 3 (4-digit) decode, level 4 (5-digit) decode, and Preferred Term). No extra table for prior Anti-TNFs will be produced due to the fact that this summary is identical to the 1 for the past Anti-TNF.

Prior medication (except DMARDs and NSAIDs) will be summarized by WHO-DRL ATC code (level 2 (3-digit) and level 3 (4-digit) decode).

Concomitant DMARDs and NSAIDs will be summarized by WHO-DRL ATC code (level 3 (4-digit) decode, level 4 (5-digit) decode, and Preferred Term) for the study as a whole and separately for those medications taken during the SFE for the SFE Safety Set.

Concomitant medication (except DMARDs and NSAIDs) will be summarized by WHO-DRL ATC code (level 2 (3-digit) and level 3 (4-digit) decode).

## 7 MEASUREMENTS OF TREATMENT COMPLIANCE

All described calculations of treatment compliance will correspond to double-blind study medication only.

There will be 2 approaches to calculate treatment compliance. The first will utilize the number of administered syringes and compare them to the scheduled expected number of injections. Two syringes will be dispensed in each kit. Both syringes should be administered for the loading doses (at weeks 0, 2 and 4) however only 1 syringe should be administered at any other visit. The difference in number of syringes between the total actual used and the total expected syringes will be summarized. For calculation of total expected syringes, all scheduled administration up to and including the last administration prior to switch to open-label CZP / other treatment or start of SFE treatment will be considered, assuming a 14 days dosing interval. If a subject continues to take double-blind medication after week 52 and prior to start of SFE following instructions from the sites, such administrations will also be included as expected syringes in the calculation.

In addition, a ratio of compliance will be further computed based on the number of actual and expected syringes. The ratio of compliance will be summarized as a continuous variable and categorically ( $<0.80$ ,  $\geq 0.80 \leq 1.0$ ,  $>1.0 \leq 1.2$  and  $>1.2$ ). The general formula for the compliance ratio (CR) is given as follows:

$$\text{CR for syringes} = \# \text{ actual syringes} / \# \text{ expected syringes}$$

The second approach defines compliance with study drug administration based upon comparing the actual day of administration with the expected day of administration. The expected day of administration will be based upon the Baseline date. The sum of the absolute difference in days between the actual and expected days will be summarized. In addition, a ratio of compliance will be further computed based upon the actual and expected day. The ratio of compliance will also be summarized as a continuous variable and categorically ( $<0.80$ ,  $\geq 0.80 \leq 1.0$ ). The general formula for the compliance ratio is given as follows:

$$\text{CR for injection day} = (\text{DB Study Duration} - \text{Cumulative Difference}) / \text{DB Study Duration}$$

The CR for injection day ranges between 0 and 1.

To calculate double-blind study duration, the date of the last injection date prior to double-blind study treatment discontinuation will be compared to the Baseline date, as shown below:

Double-blind Study Duration (days) = last DB injection date – Baseline date (maximum value is 350 days)

Cumulative Difference (days) = sum (ABS [actual date – scheduled date])

The sum will be calculated for the 26 visits from Week 0 (Baseline) to Week 50.

In case the actual day of administration is missing, the maximum deviation to the scheduled day will be assumed (ie, 14 days). If, for a scheduled day with 2 planned injections, the syringes were administered on 2 different days, the maximum day difference of the 2 actual dates to the scheduled date will be utilized.

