#### **3.5.5 Per Protocol Set**

The Per Protocol Set (PPS) will consist of subjects in the FAS without any important protocol deviations that may influence the validity of the primary efficacy data. Treatment compliance as defined in Section 7 may also be utilized. Important protocol deviations will be predefined and evaluated at the DEM prior to study unblinding at the Week 52 interim database lock. Protocol deviations occurring after Week 52 (for example, for subjects continuing in the SFE period) will not be considered for PPS impact as they occurred after assessment of the primary variable was performed.

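### The injection-day compliance ratio is not confined to 0–1 as the SAP states, because its numerator runs to Week 50 while its denominator stops at the last double-blind injection

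*SAP*

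**What the plan says.** SAP Section 7 defines two compliance measures for double-blind medication. The first compares syringes used with syringes expected, and it counts expected syringes only as far as the last administration before a switch to open-label or other treatment, or before the extension starts.

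The second measure, at issue here, compares actual with expected injection days. The ratio is the double-blind duration minus a cumulative difference, divided by the double-blind duration. Its parts are fixed as follows:

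- Duration: "the date of the last injection date prior to double-blind study treatment discontinuation will be compared to the Baseline date", and the "maximum value is 350 days".
- Cumulative difference: the sum of absolute day deviations. "The sum will be calculated for the 26 visits from Week 0 (Baseline) to Week 50".
- Missing date: "the maximum deviation to the scheduled day will be assumed (ie, 14 days").
- Expected dates: "The expected day of administration will be based upon the Baseline date".
- Stated range: "The CR for injection day ranges between 0 and 1".

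The ratio is to be summarised as a continuous variable and in two categories, below 0.80 and 0.80 to 1.0. On the Per Protocol Set (PPS), Section 3.5.5 adds: "Treatment compliance as defined in Section 7 may also be utilized". It names neither a ratio nor a cut-off.

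**The concern.** The two halves of the ratio cover different spans. The duration shrinks when a subject stops double-blind treatment early. The sum does not: it names all 26 visits and contains no stopping rule. Each injection after discontinuation has no actual date, so under the missing-date rule it costs 14 days, although it was never due. A subject who kept every appointment and then stopped is scored as a poor adherer, and the stated range fails.

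The first consequence is descriptive. The mean, the minimum and the count below 0.80 would reflect how early subjects stopped as much as how punctual they were, and a single value such as −23 could dominate a mean.

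The second consequence is conditional. Under Section 8.1, anyone who leaves double-blind treatment before Week 52 is a non-responder, and Section 8.1.3.2 expects that subjects may be taken off treatment for lack of response. If this ratio, with the tabulated 0.80 cut, were used to define the PPS, the subjects removed would be largely non-responders by definition. Membership of the set would then depend on the outcome.

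**Working it through.** **Inputs, all from SAP Section 7:** 26 visits (Weeks 0, 2, …, 50); 14-day interval; maximum duration 350 days; 14 days per missing date; ratio = (duration − cumulative difference) / duration.

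**The plan's own figures.** Weeks 0 to 50 in steps of 2 give 26 visits, and 25 intervals × 14 days = 350 days. Both reproduce. A completer with every dose on time has (350 − 0)/350 = 1.00, which is the upper bound.

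**Early stopper, otherwise exactly on time, literal rule.** Let the last double-blind injection be at Week w.

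- Duration = 7w days.
- Injections not given = 25 − w/2.
- Cumulative difference = 14 × (25 − w/2) = 350 − 7w days.
- Ratio = (7w − (350 − 7w)) / 7w = 2 − 50/w.

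| Last injection | Duration (days) | Cumulative difference (days) | Ratio |
|---|---|---|---|
| Week 0 | 0 | 350 | undefined |
| Week 2 | 14 | 336 | −23.0 |
| Week 12 | 84 | 266 | −2.17 |
| Week 24 | 168 | 182 | −0.08 |
| Week 26 | 182 | 168 | 0.08 |
| Week 40 | 280 | 70 | 0.75 |
| Week 42 | 294 | 56 | 0.81 |
| Week 50 | 350 | 0 | 1.00 |

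The ratio reaches 0 at w = 25, so it is negative for a last injection at Weeks 2 to 24. It reaches 0.80 at w = 50/1.2 = 41.7, so every last injection up to Week 40 falls below 0.80.

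**Sum stopped at the last double-blind injection.** The same on-time subject has a cumulative difference of 0 and a ratio of 1.00 for any last injection from Week 2 on. Two exceptions to the stated range remain:

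- A subject dosed only at Week 0 gives 0/0.
- If every dose from Week 2 is 15 days late, the cumulative difference is 25 × 15 = 375 days. With the duration capped at 350, the ratio is (350 − 375)/350 = −0.07.

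**Late injections under the Baseline anchor, all 26 doses given, duration capped at 350.**

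- One isolated 3-day slip: (350 − 3)/350 = 0.991.
- A 3-day shift from Week 2, never corrected: 25 × 3 = 75 days, ratio 0.786.
- The same from Week 4: 24 × 3 = 72 days, ratio 0.794.
- The same from Week 6: 23 × 3 = 69 days, ratio 0.803.

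**The case against.** The strongest reply is that the authors meant an on-treatment span throughout. Section 7 is restricted to double-blind medication, the syringe count stops at the last administration before a switch, the duration stops at the last double-blind injection, and the stated 0–1 range makes sense only if the sum stops there too. On that reading the 26 visits are simply the full schedule, parallel to the 350-day maximum, and on-time early stoppers score 1.00. This may well be the intention, but Section 7 does not say it. The limit is written out for the syringe ratio and absent from the injection-day sum. Two programmers could therefore obtain −2.17 and 1.00 for the same Week 12 stopper. Even the truncated reading leaves the range unguaranteed, as the two exceptions show.

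Three further limits stand:

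- **PPS.** Section 3.5.5 makes use of compliance optional, and Section 3.4 places the deviation criteria in a separate document. Section 8 confines the PPS to a sensitivity analysis of the primary endpoint.
- **Baseline anchor.** A reader might infer that one 3-day slip is enough to class a compliant subject below 0.80. It is not: an isolated slip gives 0.991, and only a shift starting at Week 2 or Week 4 and never corrected falls below the cut. Measuring against a calendar fixed at Baseline is a defensible design choice.
- **Other summaries.** The syringe difference and syringe ratio are unaffected, and so are the injection-day ratios of completers as far as early stopping is concerned. The compliance reporting as a whole is not invalidated.

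**Conclusion.** The stated 0–1 range is wrong for the rule as written. Read literally, an on-time subject has a negative ratio for a last injection at Weeks 2 to 24, a ratio below 0.80 for any last injection up to Week 40, and no ratio at all if dosed only at Week 0. These figures assume that injections after discontinuation count as missing dates, which is what the 26-visit sum and the missing-date rule together produce but which the SAP does not state outright. If the sum is silently truncated, the early-stopper figures disappear, but the range still fails in the two exceptional cases.

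A reader might go further and infer that the PPS analysis is biased. The document does not support that: no ratio or cut-off is fixed for the PPS, so selective exclusion of early discontinuers is a possibility only. Its size cannot be computed, because the SAP gives no discontinuation rates by arm. The Full Analysis Set primary analysis and the testing hierarchy are not affected. The correction should be made, but it does not threaten the trial's main conclusion.

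**What to change.** In Section 7:

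1. Sum the deviations only over injections scheduled up to and including the last double-blind injection, so that numerator and denominator cover the same span. The syringe ratio is already limited in this way.
2. Floor the ratio at 0, so that the stated range holds.
3. Report the ratio as not applicable for a subject with a single injection.

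In Section 3.5.5, state whether a compliance rule applies to the PPS. If it does, base it on the syringe ratio and give the cut-off.

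The Baseline anchor for expected dates can stay. The cost is a few sentences in the SAP and the reprogramming of one derived variable, with no new data.

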## 8 EFFICACY ANALYSES

All efficacy analyses of the double-blind 52-week treatment period will be performed using the FAS. The PPS and Randomized Set will be used for a sensitivity analysis on the primary endpoint only (using the composite endpoint analysis). The SFE-FAS will be used for analysis of efficacy data at the Week 156/SFE-WD visit.

The statistical analysis of the primary efficacy variable and selected secondary efficacy variables will account for multiplicity by using a fixed sequence testing procedure. The predefined order of hypotheses testing, each at a 2-sided 0.05 significance level for the comparison between CZP 200mg Q2W and placebo, will be performed in the sequence shown below. After the first test, each subsequent test is performed only if the previous test is significant in favor of CZP at the 2-sided 0.05 level. Note that the first test relates to the primary efficacy variable while the others provide the sequential testing for selected secondary efficacy variables:

Primary:

1. ASDAS-MI response at Week 52 (Composite endpoint analysis)

Secondary:

2. ASAS40 response at Week 12 (Composite endpoint analysis)
3. Change from Baseline in BASDAI at Week 12 (Reference based multiple imputation analysis)
4. Change from Baseline in BASFI at Week 12 (Reference based multiple imputation analysis)
5. ASAS40 response at Week 52 (Composite endpoint analysis)
6. Change from Baseline in BASDAI at Week 52 (Reference based multiple imputation analysis)
7. Change from Baseline in BASFI at Week 52 (Reference based multiple imputation analysis)
8. Change from Baseline in SI joint SPARCC score at Week 12 (Reference based multiple imputation analysis)
9. Change from Baseline in ASQoL at Week 52 (Reference based multiple imputation analysis)

10. Change from Baseline in nocturnal spinal pain (NRS) at Week 52 (Reference based multiple imputation analysis)

11. Number of subjects with AU or new AU flares through Week 52

Hierarchical testing of efficacy variables for Canada (and any other country where applicable or where requested by Regulatory Authorities):

Primary:

1. ASAS40 response at Week 12 (Composite endpoint analysis)

Secondary:

2. ASDAS-MI response at Week 52 (Composite endpoint analysis)

3. Change from Baseline in BASDAI at Week 12 (Reference based multiple imputation analysis)

4. Change from Baseline in BASFI at Week 12 (Reference based multiple imputation analysis)

5. ASAS40 response at Week 52 (Composite endpoint analysis)

6. Change from Baseline in BASDAI at Week 52 (Reference based multiple imputation analysis)

7. Change from Baseline in BASFI at Week 52 (Reference based multiple imputation analysis)

8. Change from Baseline in SI joint SPARCC score at Week 12 (Reference based multiple imputation analysis)

9. Change from Baseline in ASQoL at Week 52 (Reference based multiple imputation analysis)

10. Change from Baseline in nocturnal spinal pain (NRS) at Week 52 (Reference based multiple imputation analysis)

11. Number of subjects with AU or new AU flares through Week 52

The approach for handling missing values is described in [Section 4.2](#).

The primary analyses to be used in the fixed sequence testing procedure are described in [Sections 8.1](#) and [Section 8.2](#). Further sensitivity analysis and various approaches for handling missing data values are described in [Section 4.2](#).

